11.4. IMMUNOGENICITY

Immunogenicity is a measure of the immune response to a therapeutic drug (e.g. a monoclonal antibody) resulting in generation of anti-drug antibodies. Clinical samples are tested in a sequence of binding anti-drug antibody (ADA) and neutralizing antibody assays:

- Screening assay- Each sample is tested for the presence of anti-drug antibodies (ADA assay) and initially declared positive or negative according to assay cut-off criteria. Positive samples are then tested in the confirmation ADA assay. Negative samples are not tested further.
- Confirmation assay- Each positive sample from the screening assay is then confirmed positive in this assay or is declared negative. Positive samples are then tested in the neutralization (NAb) assay.
- Titration assay- Each positive sample from the confirmation assay is assessed using serial dilution to provide a titre, corresponding to the highest dilution factor that still yields a positive test result.

A table will be produced summarizing the number and percentage of confirmed positive and negative ADA samples in each treatment group in the Safety Population. The table will also be summarized the highest assay results obtained post-baseline.

A similar table will also be produced summarizing results for the neutralizing antibody assay in the Safety Population, by visit.

All immunogenicity results (i.e. ADA screening and confirmatory assay results, titre values, neutralizing antibody results will be listed.

11.5. VITAL SIGNS

Vital Signs parameters include blood pressure (systolic and diastolic), pulse rate, respiratory rate, oral/auxiliary temperature, height and weight. Vital signs assessment will be conducted at all study visits. Vital sign parameter values and changes from baseline will be summarized using descriptive statistics by visits. A by-subject listing will be provided for all vital sign parameters which includes scheduled and unscheduled visits.

11.6. 12-LEAD ELECTROCARDIOGRAM

A 12-Lead ECG will be performed at Screening, Week 0, Week 8, Week 16 and Week 24 visits. The

following ECG parameters will be assessed at each scheduled study visits:

- Heart Rate (bpm)
- QRS Interval (msec)
- PR Interval (msec)
- RR Interval (msec)
- QT interval (msec)
- QTc Interval (msec)
- QTcF (msec)
- QTcB (msec)
- Overall Interpretation

Where triplicate ECG evaluations were performed, the mean value for each subject will be used for the calculation of summary statistics. The data on QTc(B) was not collected in the CRF and will be derived using the following formula.

$$QTc(B) = \frac{QT}{\sqrt{RR/1000}}$$

Descriptive summaries will be presented for the ECG parameter values and change from baseline by visit for all quantitative measurements. Overall interpretation of ECG clinical assessment will be summarized by counts and percentages. At each timepoint, QT, QTcF and QTcB will be categorized as follows, and the category based on actual value will be summarized at each visit as well as the category at each post-baseline visit based on change from baseline per the following criteria:

| Type of Value | Category 1 | Category 2 | Category 3 |
|----------------------|------------|------------|------------|
| Actual value | > 450 ms | > 480 ms | >500 ms |
| Change from Baseline | > 30 ms | >60 ms | |

Counts and percentages for subjects with the above categories for QT, QTcF and QTcB (>450 ms, >480 ms and >500 ms) parameter values and change from baseline (>30 ms increase, >60 ms increase and >500 ms or >60 ms increase) will be summarized at each visit. A by-subject listing of all ECG parameters will be provided which includes scheduled and unscheduled visits.

12 PROGRAMMING CONSIDERATIONS

All tables, figures, listings (TFLs), and statistical analyses will be generated using SAS for Windows, Release 9.4 or higher (SAS Institute Inc., Cary, NC, USA). Computer-generated table, listing and figure output will adhere to the following specifications.

- One SAS program can create several outputs.
- Each output will be stored in a separate file.
- Output files will be delivered in Word format.
- Numbering of TFLs will follow ICH E3 guidance.
- All tables and listings will be produced in landscape orientation. Figures use the orientation that best facilitates interpretation of the data
- All TFLs will be produced using the Courier New font, size 10. The smallest acceptable point size for the Regulatory Authorities is 8.
- Headers and footers for figures will be in Courier New font, size 8 which is the smallest acceptable point size for the Regulatory Authorities.
- TFLs will be in black and white (no color), unless otherwise specified.
- The TLFs with subgroup analysis based on OCS dose at baseline Yes/No, the each subgroup category to be printed on the left side. The overall results should be presented first, followed by Baseline OCS=Yes, Baseline OCS=No.
- Specialized text styles, such as bolding, italics, borders, shading, and color are not used in the tables and listings, unless otherwise specified. Color may be used in figures containing multiple plotted lines as long as information is not lost when the figure is reproduced in monotone.
- Mixed case will be used for titles, footnotes, column headers, and programmer-supplied formats, as appropriate.
- For categorical parameters, all categories will be presented in the table, even if n=0 for all treatment groups in a given category. For example, the frequency distribution for symptom severity would appear as:

| Severity Rating | n |
|-----------------|---|
| Mild | 2 |
| Moderate | 5 |
| Severe | 0 |

- An Unknown or Missing category will be added to each parameter for which information is not available for 1 or more subjects.
- Unless otherwise specified, the estimated mean, median, Q1 and Q3 for a set of values will be printed out to 1 more significant digit than the original values, and standard deviations and standard errors will be printed out to 2 more significant digits than the original values. The minimum and maximum will report the same significant digits as the original values.
- Confidence intervals are displayed within round brackets and separated by a comma. The lower limit is presented first, and the upper limit is presented second. The confidence interval is placed either beside or below the corresponding estimate. The estimate and the confidence limits are presented using the same degree of precision.
- P-values will be output in the format: '0.xxx', where xxx is the value rounded to 3 decimal places. Every p-value less than 0.001 will be presented as <0.001. If the p-value is returned as >0.999, then present as >0.999.
- Percentage values will be printed to one decimal place. Unless otherwise noted, for all percentages, the number of subjects in the analysis population for the treatment group who have an observation will be the denominator. Percentages after zero counts will not be displayed and percentages equating to 100% will be presented as 100%, without decimal places.
- Tabular display of data for medical history, prior/concomitant medications, and all tabular displays of adverse event data will be presented by the body system, treatment class, or SOC with the highest occurrence in the active treatment group in decreasing order, assuming all terms are coded. Within the body system, drug class and SOC, medical history (by preferred term), drugs (Medication class), and adverse events (by preferred term) will be displayed in decreasing order. If incidence for more than 1 term is identical, they will then be sorted alphabetically.
- Missing descriptive statistics or p-values which cannot be estimated will be reported as '-' Missing values for numeric and character variables are displayed as blanks in data listings
- The percentage of subjects will normally be calculated as a proportion of the number of subjects assessed in the relevant treatment group (or overall) for the analysis population presented. However, careful consideration is required in many instances due to the complicated nature of selecting the denominator, usually the appropriate number of subjects exposed. Details will be described in footnotes or programming notes, as necessary.
- If no relevant data are available at all for a display, then present "No data to Report".

APPENDIX 1. MISSING DATE PROCEDURE

Prior/Concomitant Medications

For the purpose of assessing whether a medication is prior or concomitant, if a medication has a completely missing start date it will be considered a prior medication, and if a medication has a completely missing stop date it will be considered a concomitant medication. If a partial start or stop date occurs, the following imputation process will be implemented:

| Partial Missing | Imputation for Start Date | Imputation for |
|---|--|---|
| Start or Stop Date | | Stop Date |
| Day missing, month and year present | Month and/or year different to month and year of first study drug dose: Impute day with "01" Month and/or year same as month and year of first study drug dose: Impute day with same day as first dose of study drug. | Impute day with last day of the month |
| Day and month missing, year present | Year different to year of first study drug dose: Impute day and month with "01JAN" Year same as year of first study drug dose: Impute month and day with same month and day as first dose of study drug. | Impute day and month with "31DEC" |
| Month missing, day and year present | Year different to year of first study drug dose: Impute month with "JAN" Year same as year of first study drug dose: Impute month with same month as first dose of study drug. | Impute with "DEC" |
| Caveats | If any imputed start date leads to a start date that is after the start date will be imputed with the date of the stop of No stop date will be imputed if the treatment is ongoing. | f medication. |

Adverse Events

For the purpose of assessing whether an AE is on on-treatment the following imputation will be used. If the last dose of study drug is missing and the AE start date is on or after the first dose of study drug then the AE will be considered as on-treatment. If the AE start date is missing or partial then the AE will be considered on-treatment unless there is evidence to the contrary (e.g. month/year of onset date is present and is earlier than the month/year of first dose of study medication).

For assessing on-treatment or for calculation of duration of AE, if a partial start or stop date occurs, the following imputation process will be implemented:

| Partial Missing | Partial Missing Imputation for Start Date | |
|--------------------|---|----------------------|
| Start or Stop Date | | Date |
| Day missing, month | Month and/or year different to month and year of | Impute day with last |
| and year present | first study drug dose: Impute day with "01". | day of the month |
| | Month and/or year same as month and year of first | |
| | study drug dose: Impute day with same day as first | |
| | dose of study drug. | |
| Day and month | Year different to year of first study drug dose: | Impute day and |
| missing, year | Impute day and month with "01JAN". | month with "31DEC" |
| present | Year same as year of first study drug dose: Impute | |
| | month and day with same month and day as first | |
| | dose of study drug. | |
| Month missing, day | Year different to year of first study drug dose: | Impute with "DEC" |
| and year present | Impute month with "JAN". | |
| | Year same as year of first study drug dose: Impute | |
| | month with same month as first dose of study drug. | |
| Caveats | • If any imputed start date leads to a start date that is after the stop date, then | |
| | the start date will be imputed with the date of the stop | of AE. |

APPENDIX 2. CORTICOSTEROID CONVERSION FACTORS

All corticosteroids administered via oral, IV and IM routes are to be considered when calculating a subject's daily prednisone/prednisolone dose regardless of reason for administration. All steroids administered via a sublingual route will also be considered as oral.

The following corticosteroid conversion factors will be used, regardless of the route of administration, to scale each corticosteroid dose to a prednisone equivalent dose. These three routes of administration (oral, IV and IM) are to be considered equivalent as it has been noted that the bioavailability of methylprednisolone is considered to be roughly equivalent following administration as an oral, IV or IM steroid. If there are seen to be two corticosteroid records that are seen to overlap on a particular study day, these overlapping records will be summed in order to obtain a total prednisolone equivalent dose for the day in question.

| Standardized Medication Name | Scaling Factor |
|-------------------------------------|----------------|
| Betamethasone | 8.33 |
| Betamethasone Dipropionate | 8.33 |
| Betamethasone Sodium Phosphate | 8.33 |
| Cortisone | 0.2 |
| Cortisone Acetate | 0.2 |
| Cortivazol | 17 |
| Deflazacort | 0.833 |
| Dexamethasone | 6.67 |
| Dexamethasone Sodium Phosphate | 6.67 |
| Fludrocortisone Acetate | 0 |
| Hydrocortisone | 0.25 |
| Hydrocortisone Sodium Succinate | 0.25 |
| Hydrocortisone Sodium Phosphate | 0.25 |
| Meprednisone | 1 |
| Methylprednisolone | 1.25 |
| Methylprednisolone Acetate | 1.25 |
| Methylprednisolone Sodium Succinate | 1.25 |
| Methylprednisone | 1.25 |
| Methylprednisone Acetate | 1.25 |
| Prednisolone | 1 |
| Prednisolone Acetate | 1 |
| Prednisolone Hemisuccinate | 1 |

| Standardized Medication Name | Scaling Factor |
|-------------------------------|----------------|
| Prednisolone Sodium Succinate | 1 |
| Prednisone | 1 |
| Prednisone Acetate | 1 |
| Triamcinolone | 1.25 |
| Triamcinolone Acetonide | 1.25 |

APPENDIX 3. Assessment Visit Windows for eDirary Device varaibles

The following assessments will be collected daily using an eDiary device:

- Morning peak flow
- Number of occasions of usage of rescue medication (i.e. salbutamol)
- Asthma symptom score
- Frequency of awakening due to asthma symptoms requiring use of rescue medication
- ACQ scores

To derive 4-weekly average values, the following assessment visit window will be used:

| Reporting Period | First Day Included Last Day Included | |
|---------------------|--|---|
| Baseline | 7 days prior to Visit 2 | Day of first dose |
| Weeks 1-4 | Day after day of first dose | 28 days after day of first dose |
| Weeks 5-8 | 29 days after day of first dose | 56 days after day of first dose |
| Weeks 9-12 | 57 days after day of first dose | 84 days after day of first dose |
| Weeks 13-16 | 85 days after day of first dose | 112 days after day of first dose |
| Weeks 17-20 | 113 days after day of first dose | 140 days after day of first dose |
| Weeks 21-24 | 141 days after day of first dose | Week 24 visit date (or 168 days after day of first dose if earlier) |

The average 4-weekly values will be derived based on the non-missing values in the corresponding period 4-weekly period. At least 7 days of eDiary parameter data is required in the corresponding 4-weekly period to get the reliable estimate.

The ACQ scores, which are collected weekly using the eDiary device will be summarized in a weekly period using the following assessments:

| Reporting Period | First Day Included | Last Day Included | Multiple ACQ scores in period |
|--------------------|-----------------------|----------------------|-------------------------------|
| Optimisation Phase | All days prior | to study day -4 | Not to be summarised |
| Baseline | Study day -7 | Study day 1 | Take score closest to day 1 |
| Week 1 | Study day 2 | Study day 12 | Take score closest to day 8 |
| Week 2 | Study day 13 | Study day 19 | Take score closest to day 15 |
| Week 3 | Study day 20 | Study day 26 | Take score closest to day 22 |
| Week 4 | Study day 27 | Study day 33 | Take score closest to day 29 |
| Week 5 | Study day 34 | Study day 40 | Take score closest to day 36 |
| Week 6 | Study day 41 | Study day 47 | Take score closest to day 43 |
| Week 7 | Study day 48 | Study day 54 | Take score closest to day 50 |

| Reporting Period | First Day Included | Last Day Included | Multiple ACQ scores in period |
|------------------|-----------------------|----------------------|-------------------------------|
| Week 8 | Study day 55 | Study day 61 | Take score closest to day 57 |
| Week 9 | Study day 62 | Study day 68 | Take score closest to day 64 |
| Week 10 | Study day 69 | Study day 75 | Take score closest to day 71 |
| Week 11 | Study day 76 | Study day 82 | Take score closest to day 78 |
| Week 12 | Study day 83 | Study day 89 | Take score closest to day 85 |
| Week 13 | Study day 90 | Study day 96 | Take score closest to day 92 |
| Week 14 | Study day 97 | Study day 103 | Take score closest to day 99 |
| Week 15 | Study day 104 | Study day 110 | Take score closest to day 106 |
| Week 16 | Study day 111 | Study day 117 | Take score closest to day 113 |
| Week 17 | Study day 118 | Study day 124 | Take score closest to day 120 |
| Week 18 | Study day 125 | Study day 131 | Take score closest to day 127 |
| Week 19 | Study day 132 | Study day 138 | Take score closest to day 134 |
| Week 20 | Study day 139 | Study day 145 | Take score closest to day 141 |
| Week 21 | Study day 146 | Study day 152 | Take score closest to day 148 |
| Week 22 | Study day 153 | Study day 159 | Take score closest to day 155 |
| Week 23 | Study day 160 | Study day 166 | Take score closest to day 162 |
| Week 24 | Study day 1 | 67 onwards | Take score closest to day 169 |

APPENDIX 4. CLINICALLY SIGNFICANT EXACERBATIONS

Clinically significant exacerbations of asthma is defined as the worsening of asthma, which requires use of systemic corticosteroids. Exacerbations will be treated per the investigator's clinical practice protocol with the use of oral or parenteral corticosteroids.

Clinically significant exacerbations recorded in the eCRF by the Investigator or designee will be verified using data from the eDiary to confirm that the exacerbation was associated with changes in peak flow, rescue medication use, nocturnal awakening due to asthma symptoms requiring rescue medication use or worsening of asthma symptom score. In the case that an event described as a clinically significant exacerbation is not associated with deterioration in at least one of these objective eDiary parameters, the investigator will be asked to provide an explanation to support the decision for defining the event as an exacerbation. In those circumstances where the event cannot be supported by any objective assessment, the case will not be included as a protocol defined exacerbation but will be included as an investigator defined exacerbation. This verification process will be overseen by GSK clinical staff to ensure consistency.

For safety reasons alerts will be programmed into the eDiary to encourage the participant to contact the investigator if their asthma worsens. However, an alert in itself will not be classified as a clinically significant exacerbation.

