8.1.1. Efficacy Endpoints

Primary Efficacy Endpoint

Not applicable

Secondary Efficacy Endpoint

- Number of clinically significant exacerbations
- Number of exacerbations requiring hospitalization or ED visits
- Number of exacerbations requiring hospitalization
- Change from baseline in clinic pre-bronchodilator FEV₁ at week 24
- Change from baseline in clinic post-bronchodilator FEV₁ at week 24
- Change from baseline in ACQ-5 score at week 24
- Change from baseline in morning PEF during weeks 20 24

8.1.2. Number of clinically significant exacerbations (including exacerbations requiring hospitalization or ED visits)

Clinically significant exacerbations of asthma as defined by:

Worsening of asthma which requires use of systemic corticosteroids and/or hospitalisation and/or Emergency Department (ED) visits.

¹For all subjects, i.v. or oral steroid (e.g., prednisone) for at least 3 days or a single IM CS dose is required. For subjects on maintenance systemic corticosteroids, at least double the existing maintenance dose for at least 3 days is required.

Clinically significant exacerbations of asthma will be defined as the worsening of asthma which requires use of systemic corticosteroids. Exacerbation will be treated per the investigator's clinical practice protocol with the use of oral or parenteral corticosteroids.

Clinically significant exacerbations recorded in the eCRF by the Investigator or designee will be verified using data from the eDiary to confirm that the exacerbation was associated with changes in peak flow, rescue medication use, nocturnal awakening due to asthma symptoms requiring rescue medication use or worsening of asthma symptom score. In the case that an event described as a clinically significant exacerbation is not associated with deterioration in at least one of these objective eDiary parameters, the investigator will be asked to provide an explanation to support the decision for defining the event as an exacerbation. In those circumstances where the event cannot be supported by any objective assessment, the case will not be included as a protocol defined exacerbation but will be included as an investigator defined exacerbation. This verification process will be overseen by GSK clinical staff to ensure consistency.

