3.3 EXPLORATORY OBJECTIVE

4. ESTIMANDS

Primary Endpoints:

Incidence of on-treatment adverse events (AEs), serious adverse events (SAEs) and adverse events of special interest (AESIs).

The primary estimand for this endpoint is described by the following attributes:

- Population: Severe refractory asthma patients in India with elevated eosinophils.
- Treatment condition: Participants to receive Mepolizumab 100mg SC every 4 weeks during 24 weeks treatment period.
- Variable/endpoint: Incidence of on-treatment adverse events (AEs), serious adverse events (SAEs) and adverse events of special interest (AESIs).
- Summary measure: Counts and percentages for incidence of at least one AE will be summarised overall, by system organ class and by preferred term.
- Key Intercurrent events & Strategy:
 - Discontinuation of treatment (for any reason) While on-treatment strategy will be used for treatment discontinuation. This will estimate the percentage of participants experiencing an AE, while receiving treatment. AEs will be defined as on-treatment between the first dose up to and including 28 days following the last dose of mepolizumab.

Supplementary Estimand:

This supplementary estimand will report all AEs regardless of the discontinuation of study treatment.

- Population: Severe refractory asthma patients in India with elevated eosinophils.
- Treatment condition: Participants to receive Mepolizumab 100mg SC every 4 weeks during 24 weeks treatment period.
- Variable/endpoint: Incidence of AEs and SAEs
- Key Intercurrent events & Strategy:

• Treatment discontinuation (for any reason) - Treatment policy strategy will be used for treatment discontinuation. This summary will therefore be inclusive of all on-treatment and post-treatment AEs.

Secondary Endpoints:

- Number of clinically significant exacerbations (including exacerbations requiring hospitalization or ED visits)
- Number of exacerbations requiring hospitalization or ED visits
- Number of exacerbations requiring hospitalization
- Change from baseline in clinic pre-bronchodilator FEV1 at week 24
- Change from baseline in clinic post bronchodilator FEV1 at week 24
- Change from baseline in ACQ-5 score at week 24
- Change from baseline in morning PEF during weeks 20 24

The estimand for the secondary endpoint are detailed here.

- Number of clinically significant exacerbations (including exacerbations requiring hospitalization or ED visits)

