10.2. STATISTICAL METHODS FOR SECONDARY EFFIACACY ENDPOINTS

10.2.1. Asthma Exacerbations:

The number of clinically significant asthma exacerbations (including exacerbations requiring hospitalization or ED visits) that occur while on treatment will be analyzed using Negative Binomial regression using generalized linear model with a covariate of time period (pre-, post-mepolizumab as ordinal variable) with follow-up time within each period included as an offset within the model. The exacerbation rates during the pre- and post-treatment with mepolizumab will be presented, including comparison of pre- and post-mepolizumab exacerbation rates along with the with 95% confidence limits and corresponding p-value. Exacerbations separated by less than 7 days will be treated as a continuation of the same exacerbation. The following SAS code will be used:

where exbnum = number of clinically significant asthma exacerbations

period = pre- and post- mepolizumab treatment periods in which the exacerbation occurred logtime = \log_e (length of time in years in pre- mepolizumab and post- mepolizumab periods) Length of time (years) in study will be calculated as length of time (days)/365.25.

An unstructured covariance structure will be used in the model. If there are any convergence issue, then an alternative exchangeable or compound symmetric, autoregressive (AR (1)), Toeplitz covariance structure will be used. The variance of the mean estimate will be corrected for within-subject correlation by using REPEATED statement for subject in the GENMOD procedure.

The period of time for which exacerbation information will be included in the post-mepolizumab period will be from the start of treatment until the week 24 visit, regardless of treatment discontinuation. For

those participants with premature study withdrawal, the time period will include from the start of treatment until the date of withdrawal. Missing data (following early withdrawal) will be assumed to be missing at random (MAR) following subject withdrawal from the study.

In addition, a similar analysis will be conducted for frequency of exacerbations requiring hospitalization or ED visits and frequency of exacerbations requiring hospitalization if there are enough subjects in the corresponding category.

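### SAP Appendix 4 defines a clinically significant exacerbation by steroid use alone, against the SAP's own endpoint wording and one of two conflicting definitions in Protocol 8.1.2; one exacerbation output also counts never-treated people

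*SAP*

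**What the plan says.** **Protocol 8.1.2** opens with a broad definition: "Worsening of asthma which requires use of systemic corticosteroids and/or hospitalisation and/or Emergency Department (ED) visits". A footnote sets a minimum for the steroid treatment: three days of intravenous or oral steroid or one intramuscular dose, and for maintenance users "For subjects on maintenance systemic corticosteroids, at least double the existing maintenance dose for at least 3 days is required". The same section then says: "Clinically significant exacerbations of asthma will be defined as the worsening of asthma which requires use of systemic corticosteroids". That second sentence has no hospital or ED limb.

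**SAP Appendix 4** carries only the second form, "Clinically significant exacerbations of asthma is defined as the worsening of asthma, which requires use of systemic corticosteroids", and omits the footnote.

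**Endpoint wording in the SAP.** Section 4 lists "Number of clinically significant exacerbations (including exacerbations requiring hospitalization or ED visits" and section 10.2.1 analyses "The number of clinically significant asthma exacerbations (including exacerbations requiring hospitalization or ED visits". The list in SAP 10.1.2 and the one in Protocol 8.1.1 name the endpoint without the parenthesis. The model in SAP 10.2.1 has one outcome variable: "exbnum = number of clinically significant asthma exacerbations".

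**Other uses of the term.** SAP 7.2.8 uses it to decide asthma control in Weeks 20-24. SAP 10.7 uses it to trigger a worst-case imputation for oral corticosteroid (OCS) reduction.

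**Population.** SAP 10.2.1 plans counts and percentages of people with exacerbations in the Safety Population. It then repeats that output regardless of treatment discontinuation, and says that people who passed screening, received no treatment and discontinued are counted too. SAP 6.2 limits the Safety Population to people with at least one dose and uses it for all efficacy analyses.

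**The concern.** A programmer who follows Appendix 4 literally leaves out a hospital or ED exacerbation treated without systemic steroids, and counts any systemic steroid use for worsening asthma, however short. A programmer who follows section 10.2.1 and the first definition in Protocol 8.1.2 does the reverse on both. Each can cite current text. Under the literal appendix, the hospital/ED endpoints need not be subsets of the first endpoint, although its wording says that they are included in it.

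The missing footnote matters in its own right. OCS use and dose changes are left to the investigator (Protocol 4.1.2 and 6.5.2), and results are reported by baseline maintenance OCS use (SAP 10.5). The dose-doubling rule concerns only maintenance users, so dropping it bears on one subgroup and not the other.

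At stake is the first secondary efficacy endpoint in an open-label, single-arm, before/after comparison. A definition settled after the data are seen would be open to the charge of being chosen on the results.

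**Working it through.** **1. The definitions side by side**

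| Event | Protocol 8.1.2, first definition with footnote | Protocol 8.1.2, second definition | SAP Appendix 4 | SAP 4 and 10.2.1 wording |
|---|---|---|---|---|
| Steroid course meeting the footnote | counts | counts | counts | counts |
| Hospital/ED exacerbation, no systemic steroid | counts | does not count | does not count | counts |
| Steroid use below the footnote minimum, no hospital/ED visit | does not count | counts, unless the footnote is carried over | counts; no minimum stated | not stated |

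The last two rows disagree. Appendix 4 removes one kind of event and admits another, so the effect on the count has no determinable sign.

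**2. Does a precedence rule settle it?** SAP section 2 says that differences in the SAP supersede the protocol's analysis. That cannot decide between Appendix 4 and sections 4 and 10.2.1, which are all in the SAP. Nothing marks Appendix 4 as a deliberate change.

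**3. What one event is worth.** The plan gives no figure for this, so none can be reproduced. SAP 7.2.6 counts Week 24 date minus Week 0 date plus 1, which is 168 + 1 = 169 days for a completer on schedule.
- On-study time for 100 completers: 100 x 169/365.25 = 46.27 person-years.
- History time: 100 x 1 year = 100 person-years.
- One reclassified on-study event moves the on-study rate by 1/46.27 = 0.0216 per year.
- One reclassified history event moves the history rate by 1/100 = 0.0100 per year.
- If 5 on-study events and no history events were reclassified, the ratio would move by 5/(46.27 x history rate): 0.108, 0.054 or 0.036 at assumed history rates of 1, 2 or 3 per year.

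**4. Effect on the rate ratio.** Take events under the first definition as the base. Let a be the share lost under Appendix 4 (hospital/ED without steroid) and b the below-minimum steroid events gained, as a share of the same base. The ratio is multiplied by

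(1 - a_on + b_on) / (1 - a_hist + b_hist).

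- Equal shares, for example a = 0.05 and b = 0.10 in both periods: 1.05/1.05 = 1.00. Both rates rise by 5% and the ratio stays put.
- Opposite extremes with a of 0 or 0.05 and b of 0 or 0.10: 0.95/1.10 = 0.86 and 1.10/0.95 = 1.16.

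All values of a and b are assumptions. The extremes need the shares to differ between periods in opposing directions, and no passage says that they do.

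**5. Reach of the term.** In the table list (SAP Appendix 5), the Weeks 20-24 asthma-control rule appears only in the OCS-reduction tables 14.2.1.1 and 14.2.1.6, and the SAP 10.7 imputation serves the same outputs. Protocol 4.2 limits the OCS-sparing assessment to people who completed or withdrew before Amendment 4. The size of that subset is not given. Exploratory text is removed, so further uses cannot be checked.

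**6. Never-treated people.** The instruction conflicts with SAP 6.2 (at least one dose), SAP 7.2.6 (assessment starts at the Week 0 visit) and the exacerbation table titles in SAP Appendix 5 (all Safety Population). How many people it touches is not stated. The screening sum 154 x 0.65 = 100 does not help: the 35% covers everyone lost between screening and treatment, so it cannot isolate those who passed and were not dosed. As an illustration, suppose 30 of 100 treated people had an event (30.0%). Adding 5, 10 or 20 undosed people without events to the denominator gives 30/105 = 28.6%, 30/110 = 27.3% or 30/120 = 25.0%.

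**The case against.** The best reply is that the gap is mostly verbal. Protocol 8.1.2 and SAP Appendix 4 both go on to say that exacerbations will be treated with oral or parenteral corticosteroids, so a hospital or ED event without them may be rare. SAP 10.2.1 already tells the programmer to include hospital and ED exacerbations. The footnote could be read as explaining the same steroid requirement that Appendix 4 repeats, in which case silence is not removal. The endpoint is secondary and no hypothesis is formally tested.

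Much of this stands, and it limits the size of the problem. It does not remove the contradiction. Treatment of exacerbations is left to clinical practice (Protocol 4.1.1.1 and 4.1.2.1), so the class of events without steroids is not shown to be empty. An appendix that defines the term should not need to be overridden by the paragraph that uses it.

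A reader might also infer that events are ascertained unfairly, because on-study events are checked against an eDiary that starts at Visit 1 and the 12-month history cannot be. That is a limitation of the declared before/after design, not an error in the plan. Nor is an eDiary mismatch enough to drop an event: the investigator may explain it, and only an event with no objective support leaves the protocol-defined set.

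**Conclusion.** The point holds as a conflict of definitions, plus one wrong population instruction. Protocol 8.1.2 contradicts itself, and SAP Appendix 4 contradicts SAP sections 4 and 10.2.1, so `exbnum` can be built in two ways. The shorter endpoint lists in SAP 10.1.2 and Protocol 8.1.1 make the wording less uniform but do not resolve the conflict.

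The size is unknown and may be small. A reader might infer that the rate ratio is biased, perhaps in favour of mepolizumab. The documents do not support this: they give no count of affected events, the two effects of Appendix 4 oppose each other, and equal shares leave the ratio unchanged. The 0.86 to 1.16 range shows sensitivity to assumed unequal shares; it is not an estimate. Nor does the asthma-control rule spread the problem widely, since it visibly serves only OCS outputs for a subset.

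The never-treated sentence affects one descriptive output. The rate ratio is not touched. This should be corrected before database lock, but it does not threaten the primary safety objective.

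**What to change.** (a) Before database lock, reconcile Protocol 8.1.2 and SAP Appendix 4. Appendix 4 should carry a single analysis definition that agrees with the endpoint wording, with hospital and ED exacerbations included, and should state whether the Protocol 8.1.2 steroid footnote applies. Use that definition in both periods as far as the recorded history allows, and for the rules in SAP 7.2.8 and 10.7.

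(b) Delete the sentence in SAP 10.2.1 that counts participants who were never treated.

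The cost is SAP wording now and a correction to Protocol 8.1.2 at the next amendment. No new data or tables are needed. A sensitivity rate ratio using all investigator-defined on-study events would be a reasonable extra from data already collected, but it is optional and not part of the correction.
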